1. History of ligament, meniscal surgery or fracture on the affected knee
2. Pregnancy or breastfeeding women

IV.3. FEASIBILITY AND RECRUITMENT PROCEDURES

The study will be conducted at the Clinique Juge Orthopedic Surgery Department in association with [name]. The service already has a systematic and standardized follow-up of the patient with an ACL lesion developed according to the recommendations in good clinical practice.

The site is currently doing more than 100 ACL reconstructions a year. The service will recruit a maximum of 56 patients. All patients recruited will be patients requiring ACL reconstruction and who will receive the Composite Interference Screw manufactured by Biomatlante. The indication of treatment (surgical or not) will not be influenced by the study and will be performed according to good clinical practice.

The inclusion of patients is scheduled for a maximum of 12 months.

Patients fulfilling the study criteria will be offered to participate in the study. Those who accept will be assigned an identification number. This number will be re-used on all documents related to the study in order to preserve the patient's anonymity on these documents.

IV.4. ACTIONS UPON PATIENT WITHDRAWAL

If a patient withdraws prematurely from the study, study personnel should make every effort to complete the full panel of assessments scheduled until the 7-months visit. The reason for patient withdrawal must be documented in the electronic Case Report Form (eCRF).

Participation of a patient in this clinical study may be discontinued for any of the following reasons:

- The patient withdraws consent or requests discontinuation from the study for any reason;
- Occurrence of any medical condition or circumstance that exposes the patient to substantial risk and/or does not allow the patient to adhere to the requirements of the protocol;
- Any SAE, clinically significant adverse event, which indicates to the Investigator that continued participation, is not in the best interest of the patient;
- Pregnancy;
- Patient failure to comply with protocol requirements or study-related procedures; or
- Termination of the study by the Sponsor or the regulatory authority.

In the case of patients lost to follow-up, attempts to contact the patient must be made and documented in the patient's medical records. Withdrawn patients will not be replaced.

V. TREATMENT/ STRATEGY(IES)/ PROCEDURE(S) OF THE RESEARCH

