- Probably Related: There is evidence to suggest a causal relationship, and the influence of other factors is unlikely. The clinical event, including an abnormal laboratory test result, occurs within a reasonable time after administration of the study intervention, is unlikely to be attributed to concurrent disease or other drugs or chemicals, and follows a clinically reasonable response on withdrawal (dechallenge). Rechallenge information is not required to fulfill this definition.
- Potentially Related: There is some evidence to suggest a causal relationship (e.g., the event occurred within a reasonable time after administration of the trial medication). However, other factors may have contributed to the event (e.g., the participant's clinical condition, other concomitant events). Although an AE may rate only as "possibly related" soon after discovery, it can be flagged as requiring more information and later be upgraded to "probably related" or "definitely related", as appropriate.
- Unlikely to be related: A clinical event, including an abnormal laboratory test result, whose temporal relationship to study intervention administration makes a causal relationship improbable (e.g., the event did not occur within a reasonable time after administration of the study intervention) and in which other drugs or chemicals or underlying disease provides plausible explanations (e.g., the participant's clinical condition, other concomitant treatments).
- Not Related: The AE is completely independent of study intervention administration, and/or evidence exists that the event is definitely related to another etiology. There must be an alternative, definitive etiology documented by the clinician

VI.3.3.3. Expected adverse events

The most frequent adverse events expected from Composite Interference Screw observed in patients are:

- Postoperative infection
- Irritation
- Allergy
- Reduced patient mobility
- Pain
- Fever
- Inflammatory reaction

Certain adverse events can be treated with medicines or may require additional surgery.

VI.3.4. ADVERSE EVENTS REPORTING

Complete and accurate data on all AEs experienced for the duration of the reporting period, will be reported in the eCRF.

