In the case of a new medical fact, the Sponsor, will be responsible for reporting new facts to the authorities in accordance with national regulations, as follows:

- Inform without delay the ANSM about the new medical fact, at the following email address: [contact] with the following subject: Fait nouveau / trial number/ international non-proprietary name (INN) or substance code and including:
 - ID-RCB N°,
 - Title of the study protocol,
 - Protocol code number,
 - Summary of the new fact and urgent safety measures implemented if necessary,
 - All relevant information for the evaluation of the new fact.
- Inform without delay the director of the Agence Régionale de Santé (ARS; regional health agency) and the Ethics Committee (CPP).

Any follow-up information with regards to the new safety medical fact will be reported to the regulatory authorities within 8 calendar days, and details regarding the urgent safety measures set up will be sent within 15 days to the regulatory authorities.

VII. STATISTICAL ASPECTS

VII.1. SAMPLE SIZE DETERMINATION

The sample size required for the study was determined in order to obtain sufficient final statistical power considering the 2 main criteria (co-primary endpoint). The statistical power used to determine the sample size required for each of the 2 main criteria is 90% to obtain a final statistical power of at least 80%.

Subjective IKDC:

The minimum relevant difference expected in the change at 7 months on the functional IKDC score is 11 points and the standard deviation expected in the IKDC score at pre-surgery and at 7 months is 13 points. A total of 32 evaluable patients will be necessary to ensure a 90% power to detect a significant difference in the change at 7 months for two-sided test at the 5% level using paired Student t test.

Objective IKDC:

It is expected that 96% of patient will have modalities C or D before surgery [5]. Based on the investigator's experience, the proportion of total expected to shift from an IKDC modalities C or D to modalities A or B is 70% and proportion of total expected to shift from an IKDC modalities A or B to modalities C or D is 1%. A total of 11 evaluable patients will be necessary to ensure a 90% power to detect a significant difference for two-sided test at the 5% level using McNemar test.

In order to ensure sufficient statistical power for both comparisons, the larger of the two required sample size is planned to be included, i.e. 32 patients.

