However, to increase the estimate precision of the co-primary endpoint, 50 completed patients will be targeted. With 50 patients, a precision around 13% can be achieved for the objective IKDC score and 3.6 points for the subjective IKDC score. This sample size will provide a final statistical power for primary objective of 97%.

Accounting for a maximum of 10% dropouts or missing data, 56 patients should be recruited in the study.

VII.2. ANALYSIS SETS

Four populations will be defined:

- Screened population will include all patients entering the study,
- Safety Set (SS) population will include all patients who received the surgical intervention,
- Full Analysis Set (FAS) population will be defined by all patient who received the CIS product and in whom at least one efficacy information has been collected after the application of the CIS,

- Per-Protocol (PP) efficacy population will include all patients in FAS population without any major protocol deviation.

Remark: according to the ICH E9 recommendations, this subset of patients corresponds to a subset of the full “intention-to-treat” analysis set, being the Full Analysis Set (FAS).

VII.3. MISSING VALUES AND DROP-OUT

For the primary analysis (FAS analysis), in the case of a patient with missing data, the corresponding data will not be replaced.

For sensitivity analyses, some of the missing data may be replaced. It will be performed according to the following scenarios:

- Best-worst scenario: the missing data on the pre-surgery objective IKDC score will be considered with an objective IKDC score to A and missing data on the 7-months objective IKDC score will be considered with an objective IKDC score to D.
- Worst-best scenario: the missing data on the pre-surgery objective IKDC score will be considered with an objective IKDC score to D and missing data on the 7-month objective IKDC score will be considered with an objective IKDC score to A.
- Last Observation Carry Forward (LOCF) method: the missing data on the 7-months subjective IKDC will be replaced using LOCF method.

No other missing data will be replaced.

VII.4. STATISTICAL ANALYSIS

VII.4.1. GENERAL CONSIDERATION

A Statistical Analysis Plan (SAP) will be written by the biostatistician detailing the statistical analysis. This document will be approved and signed by the Sponsor and the Coordinating Investigator before the first database lock.

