The statistical analysis will be performed on SAS® version 9.4 or later (or equivalent statistical software).

➤ Descriptive statistics

Quantitative variables will be described by the number of values entered, the number of missing data, the mean, the standard deviation, the 95% CIs for the means, the median, the 1st and 3rd quartiles, the minimum and maximum.

Qualitative variables will be described by the number of data filled in, the number of missing data, the frequency and the percentage of each modality. The 95% CIs of the percentages will be performed using exact confidence limits method.

All variable in the database will be described using descriptive statistics and all individual data will be presented in listings.

➤ *Inferential test*

All tests will be two-sided and the type I error (α) will be set at 5%.

Quantitative score at 7-months visit will be compared to the score before surgery using paired Student t test or Wilcoxon test (depend of normality assumption).

Qualitative score at 7-months visit will be compared to the score before surgery using McNemar test or Q Cochrane test (if expected sample size for the contingency cell are less than 4).

One interim analysis and no sub-group analysis will be planned.

➤ *Pre-analysis review of patient data*

Following the ICH guideline E9, a data review meeting will be held before the final database locking. The following items will be discussed:

- By-patient, list of protocol violations and other issues with the data, and definition of the analysis sets,
- Need for amendment to the SAP, based on newly gained research information and on the examination of the data.

If required, the SAP will be amended. Data discrepancies detected at the pre-analysis data review meeting will be resolved. Subsequently, the database will be locked, and the analyses will be performed.

➤ *Protocol deviations*

A protocol deviation is any noncompliance with the clinical trial protocol, International Conference on Harmonisation Good Clinical Practice (ICH GCP), or manufacturer recommendation requirements. As a result of deviations, corrective actions are to be developed by the site and implemented promptly. It is the responsibility of the site investigator to use continuous vigilance to identify deviations. All deviations must be reported in study source documents.

All protocol deviations will be listed before the data review meeting and reviewed during this meeting and classified as “minor” or “major”.

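### The primary analysis has no rule for graft or fixation failure, or re-operation of the study knee, before month 7, so the reported success rate can be optimistic

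*Protocol*

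**What the plan says.** All places are in the protocol; the statistical analysis plan is not at hand.

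- **Withdrawal (IV.4).** Among the reasons for which participation may be discontinued is "Any SAE, clinically significant adverse event, which indicates to the Investigator that continued participation, is not in the best interest of the patient". The same section asks staff to make every effort to complete the assessments up to the 7-month visit after a premature withdrawal.
- **Missing data (VII.3).** For the primary FAS analysis, "in the case of a patient with missing data, the corresponding data will not be replaced". In sensitivity analyses, the best-worst scenario sets a missing 7-month objective IKDC to D, and last observation carried forward (LOCF) fills a missing 7-month subjective score.
- **Analysis set (VII.2).** The FAS requires the screw plus at least one item of efficacy information collected after implantation. The per-protocol set is a subset of the FAS. The first scheduled efficacy assessment after surgery is at 2 months (III.3).
- **Primary comparison (VII.4.2).** Scores recorded at 7 months are compared with those before surgery. No exception is made for a knee operated on again in between.
- **Further surgery (VI.3.3.3).** "Certain adverse events can be treated with medicines or may require additional surgery".
- **Claim and hypothesis.** V.3 claims that the screw holds the graft in the tunnel until bone consolidation is complete. I.3 expects at least 70% of the patients who undergo the reconstruction to move from C or D to A or B.

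**The concern.** Loss of graft fixation is the event that would contradict the performance claimed in V.3. Read together, VII.2, VII.3 and VII.4.2 do not ensure that it counts against the device. A failed knee can take three routes:

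1. **No 7-month score.** The patient has no complete pair and leaves the primary comparison. If the failure comes before the 2-month visit and no efficacy information was collected, the patient is outside the FAS altogether.
2. **Revised before month 7, then scored.** The score describes the second operation. An A or B is counted as improvement after reconstruction with the screw.
3. **Not revised, examined at month 7.** Under VI.1 the worst of the three item groups decides the grade, so the knee is graded as found and can be C or D.

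Only the third route counts the failure in the primary analysis. The first two push the estimated success rate upwards. That estimate matters here: there is no control arm, I.3 sets a 70% expectation for operated patients, VII.1 raises the target from 32 to 50 completers for precision, and XII.1 says the data are mainly for regulatory use.

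**Working it through.** **Inputs from VII.1.** Two-sided 5% level; 90% power per criterion. Subjective score: a relevant change of 11 points, with an SD of 13 points for the score at each of the two time points. Objective score: 70% shift from C/D to A/B, 1% the other way. 50 completers, 56 recruited (10% loss).

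**The plan's own figures first**

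- Subjective: with no correlation between the two time points, the SD of the change is 13 × √2 = 18.38. A paired t-test (noncentral t) for 11 points has power 0.897 with 31 patients and 0.906 with 32, so N = 32, as stated.
- Objective (McNemar, Connor formula): discordant share 0.70 + 0.01 = 0.71, difference 0.69. N = (1.960 × √0.71 + 1.282 × √(0.71 − 0.69²))² / 0.69² = 10.8, so 11, as stated.
- Recruitment: 50 / 0.90 = 55.6, so 56, as stated.
- Joint power with 50: 0.986 × more than 0.999 ≈ 0.986, against 97% stated. The difference does not bear on this point.

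**Effect on the success rate.** The protocol gives no rate of failure or re-operation. I assume f = 0 to 6, because 56 − 50 = 6 is the planned loss, and an observed result of 35/50 = 70.0%.

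(a) The f failures were dropped. Counting them gives 35 / (50 + f). (b) The f failures are among the 35 because they were graded A or B after revision. Counting them gives (35 − f) / 50.

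| f | (a) dropped | (b) scored after revision |
|---|---|---|
| 0 | 35/50 = 70.0% | 35/50 = 70.0% |
| 1 | 35/51 = 68.6% | 34/50 = 68.0% |
| 3 | 35/53 = 66.0% | 32/50 = 64.0% |
| 6 | 35/56 = 62.5% | 29/50 = 58.0% |

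The largest overstatement is 70.0 − 62.5 = 7.5 points under (a) and 70.0 − 58.0 = 12 points under (b). The stated precision with 50 patients is about 13 points. The exact 95% interval for 35/56 is 48.5% to 75.1%.

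**Effect on the tests**

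- McNemar: a knee that is C/D before surgery (96% expected) and D at month 7 is a concordant pair and does not enter the test. With one reverse shift, case (a) stays at 35 against 1, exact p ≈ 1 × 10⁻⁹. Case (b) with f = 6 becomes 29 against 1: p = 2 × (1 + 30) / 2³⁰ ≈ 6 × 10⁻⁸. Even if all six failures in (a) had been A/B before surgery, 35 against 7 gives p ≈ 0.00002.
- Paired t, case (a), failures set to no change: mean 11 × 50/53 = 10.4 (f = 3) or 11 × 50/56 = 9.8 (f = 6). The variance is w × 338 + w(1 − w) × 121 with w = 50/(50 + f), so the SD is 18.0 or 17.7. Power is 0.984 or 0.983.
- Paired t, case (b), f = 6 of 50: mean 11 × 44/50 = 9.7, SD 17.6, power 0.968.

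**Reach of the sensitivity analyses.** Subjective scores are scheduled only before surgery and at month 7 (III.3), so LOCF carries the pre-surgery value, a change of zero. Best-worst sets D. Both act only on missing scores, and a revised knee that has a 7-month score is not missing.

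**The case against.** The case on the other side is substantial.

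- **Withdrawal is discretionary, and follow-up continues.** A reader might infer that IV.4 sends failures out of the analysis. It does not: participation may be discontinued, and assessments to month 7 are still to be attempted. This stands. It narrows the first route, but obtaining a month-7 score leaves the revised-knee route open.
- **Some failures do count.** A reader might infer that no failure of the screw is counted. The third route shows otherwise, and the events are also recorded and tabulated as adverse events.
- **Missing scores are stress-tested.** Best-worst and LOCF already apply the unfavourable value. This stands for patients in the FAS, as sensitivity analyses only.
- **70% is not a pass mark.** VII.4.2 defines success as significance on both endpoints. This stands: a result slipping below 70% does not change the trial's formal conclusion.
- **Additional surgery in VI.3.3.3** follows a list (infection, pain, inflammatory reaction and others) that does not name graft or fixation failure. This is fair. The sentence shows that re-operation is foreseen, not how often or for what.
- **Attribution.** V.5 uses the screw in the tibia only, with an Endobutton in the femur, so a femoral failure is not the screw's. This stands and shapes the fix.
- **The analysis plan may handle it.** It could specify how a score after re-operation is used. But VII.3 already fixes the non-replacement rule for the primary analysis, so counting a missing score as failure there would contradict the protocol.

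**Conclusion.** The point holds as a gap in the primary analysis. A failed reconstruction without a month-7 score is left out, and one that is revised and then scored is analysed on the revised knee. A failed knee left unrevised and examined at month 7 is graded as found. The sensitivity analyses cover missing scores in the FAS and do not reach revised knees.

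The consequence is an optimistic success rate beside the 70% expectation in I.3: by up to 7.5 points if failures are dropped, or 12 points if they are graded A or B after revision. Both figures assume up to 6 failures and an observed 35/50; the second also assumes that every revised knee reaches A or B by month 7. With no failures there is no bias. A reader might infer that the co-primary tests themselves are at risk. On the plan's own assumptions they are not: the McNemar result stays far below 5% and the power of the paired test stays near 0.97 to 0.98.

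**What to change.** In VII.2 to VII.4.2:

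- In the primary FAS analysis, count graft or fixation failure, or re-operation of the study knee for a graft or screw problem before the 7-month visit, as objective IKDC D at 7 months.
- Use no post-revision score for either co-primary. Set the subjective 7-month score of such a patient to the pre-surgery value.
- Treat such an event as efficacy information, so that a failure before the 2-month visit stays in the FAS.
- Report the number of these failures beside the co-primaries, separating tibial (screw) from femoral (Endobutton) fixation failures.
- Show the as-observed analysis as a sensitivity analysis.

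IV.4 needs no change, because it already asks for assessments to be completed up to month 7.

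Cost: wording only. No visit, treatment or sample size changes, and the events are already collected as adverse events. The downside is a slightly less favourable success rate, and some failures not caused by the screw will count against it; the tibial/femoral split makes that visible.

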- To evaluate the safety of the use of these screws by recording all adverse events that occurred during the study
- To follow the patient's recovery through a clinical examination at 2 months post-surgery (± 2 weeks)

III. RESEARCH DESIGN

III.1. CLASSIFICATION OF THE STUDY

This clinical investigation is monocentric (Clinique Juge, Orthopedic Surgery Department), prospective, single arm and intra-subject comparative.

The study is classified as category 3 (non-interventional study) according to the Jardé law Law (French Law relative to the Clinical Research Involving Human Persons).

Indeed, according to the terms of the protocol established in collaboration with the stakeholders, this research will be carried out on a CE-marked device (CE 0123) and does not involve any risk or constraint since all the procedures will be performed and the products used in a usual way, without any additional or unusual diagnostic, treatment or monitoring action.

III.2. THE RESEARCH PROJECT AGENDA

- Duration of the inclusion period: 12 months.
- Duration of follow-up per participant: maximum 12 months (at most 4 months before surgery and 8 months of follow-up).
- Total duration of the research: 24 months.

III.3. SUMMARY TABLE OF THE PARTICIPANT FOLLOW-UP

	Before surgery V-1	Surgery V0	At discharge V1	At 2 months V2	At 7 months V3
-4 months to Day 0		D0	D0	±2 weeks	±1 month
Full information and consent	X				
Inclusion / exclusion criteria	X	X			
Demographic data	X				
Patient information ^a	X				
Life habits ^b	X				
Relevant medical and surgical histories	X				
ACL RECONSTRUCTION					
Batch		X			
Medical device for femoral fixation		X			
Clinical indication		X			
PERFORMANCE					
Visual clinical examination ^c				X	
IKDC questionnaire					
- Subjective evaluation	X				X
- Objective evaluation	X			X ^d	X
SAFETY					
AEs	X<----->X				

a. Patient information: height, weight, affected knee

b. Life habits: smoker, sport activities

c. Visual clinical evaluation: healing at the surgical site, walking test, quadriceps lock, articular amplitude (measured with a goniometer)

d. Evaluation of 2 items of the IKDC questionnaire at 2 months: Lachmann test and joint effusion items

III.4. INFORMATION OF THE PERSONS CONCERNED

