- An important medical event: AE that may not result in death, be life-threatening, or require hospitalization may be considered an SAE when, based upon appropriate medical judgment, they may jeopardize the patient and may require medical or surgical intervention to prevent one of the outcomes listed above.

The Investigator must continue to follow the patient until the SAE has subsided or until the condition becomes chronic in nature, stabilizes (in the case of persistent impairment), or the patient dies.

VI.3.3. CLASSIFICATION OF AN ADVERSE EVENT

VI.3.3.1. Severity of event

The severity of AEs must be assessed by the Investigator according to the following definitions. The term “severity” is used to describe the intensity of a specific event. This has to be distinguished from the term “serious”.

- Mild: Events require minimal or no treatment and do not interfere with the participant’s daily activities
- Moderate: Events result in a low level of inconvenience or concern with the therapeutic measures. Moderate events may cause some interference with functioning.
- Severe: Events interrupt a participant’s usual daily activity and may require systemic drug therapy or other treatment. Severe events are usually potentially life-threatening or incapacitating. Of note, the term “severe” does not necessarily equate to “serious”.

VI.3.3.2. Relationship to study product

The clinician must always determine the relationship between all adverse events and the investigated medical device by the examination and evaluation of the participant on the basis of temporal relationship between the AE and application of the device and his/her clinical judgment. In a clinical trial, the investigated medical device must always be suspected. The degree of certainty about causality will be graded using the categories below:

- Definitely Related: There is clear evidence to suggest a causal relationship, and other possible contributing factors can be ruled out. The clinical event, including an abnormal laboratory test result, occurs in a plausible time relationship to study intervention administration and cannot be explained by concurrent disease or other drugs or chemicals. The response to withdrawal of the study intervention (dechallenge) should be clinically plausible. The event must be pharmacologically or phenomenologically definitive, with use of a satisfactory rechallenge procedure if necessary.

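### Adverse events are graded once, against the screw, on a drug-type causality scale, so the relationship table cannot reliably separate screw-related from procedure-related events

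*Protocol*

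**What the plan says.** Section II.2 sets a secondary objective for the device itself: "To evaluate the safety of the use of these screws by recording all adverse events that occurred during the study". The causality rules are in VI.3.3.2. "The clinician must always determine the relationship between all adverse events and the investigated medical device", and this is done by examining the participant, "on the basis of temporal relationship between the AE and application of the device and his/her clinical judgment". A presumption is added: "In a clinical trial, the investigated medical device must always be suspected".

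Five categories follow:

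- *Definitely Related*: the event "cannot be explained by concurrent disease or other drugs or chemicals", and the response to withdrawal should be plausible, with rechallenge if needed.
- *Probably Related*: other influences are unlikely, and the event responds reasonably to withdrawal.
- *Potentially Related*: some evidence of causation, with one example ("e.g., the event occurred within a reasonable time after administration of the trial medication"); other factors may have contributed.
- *Unlikely to be related*: the timing makes causation improbable, and the event is one "in which other drugs or chemicals or underlying disease provides plausible explanations"; the participant's condition and other concomitant treatments are given as examples.
- *Not Related*: the event is independent of the intervention or definitely due to something else, with a definitive alternative cause documented.

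Section V.5 states that the graft is taken from the hamstrings, that the femoral side is fixed with an Endobutton, and that the screw is used on the tibial side only. Section VI.3.4 requires each report to note other possible causal factors. Section VII.4.4 summarises treatment-emergent events by relationship to study treatment, among other breakdowns.

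**The concern.** The scale suits a drug that can be stopped and restarted and whose administration is separate in time from other causes. Neither holds for a resorbable screw implanted during a ligament reconstruction. Harvest, tunnels, femoral device and screw share one date, so the timing criterion that runs through the scale carries almost no information about which of them caused an event.

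The study has one arm (III.1), so no control group shows the background morbidity of the operation. The causality grade is the planned means of setting the screw apart from the surgery. Section I.2 says that resorbable screws provoke inflammatory reactions that have been described but not quantified. If such reactions and ordinary postoperative inflammation receive the same grade, the table can err in two ways: it can make the screw look worse than it is, and it can hide a real screw effect among surgical events.

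**Working it through.** No arithmetic applies; the check is to trace events through the stated definitions.

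**Event A: non-specific pain, fever or stiffness a few days after surgery, with no proven cause.**

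1. *Unlikely*: two conditions are joined by *and*. The first, improbable timing, fails because the screw was implanted days earlier. The category is closed on its wording, however plausible the surgical explanation.
2. *Not Related*: open only if a definitive other cause is documented. The operation could serve as that cause, but non-specific events often lack definitive proof.
3. *Definitely* and *Probably*: both look to the effect of withdrawal, and a fixed resorbable implant is not ordinarily withdrawn. *Definitely* also requires other contributing factors to be ruled out, and *Probably* requires their influence to be unlikely.
4. *Potentially*: compatible timing is the example of evidence offered, and the event has it. Contribution from other factors is allowed.

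Of the five categories, *Potentially Related* is the one that readily fits.

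**Event B: a genuine inflammatory reaction to the screw.**

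1. *Unlikely* and *Not Related* do not apply.
2. *Probably* requires a response to withdrawal that would not normally be observed. *Definitely* refers to dechallenge and, where necessary, rechallenge.
3. *Potentially* is again the natural grade.

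Events A and B thus tend towards the same cell although their causes differ.

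**Which alternative causes are named?** Across the categories: concurrent or underlying disease, other drugs or chemicals, the participant's clinical condition, and other concomitant events or treatments. Surgery, harvest, tunnels and the femoral device are not named, although the generic terms could be stretched to cover them.

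**What is the grade relative to?** VI.3.3.2 speaks of the medical device, the study intervention and the trial medication; VII.4.4 tabulates against study treatment. The Synopsis describes the intervention as fixing the graft to reconstruct the ligament. A reader could take *study intervention* to mean the procedure, in which case a purely surgical event would not be independent of it.

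**Does another section repair this?** VI.3.4 captures other causal factors per event, and individual data are listed (VII.4.1, VII.4.8). VII.4.4 describes no table that uses those factors. VI.3.3.3 lists postoperative infection, pain, fever, reduced mobility and inflammatory reaction as expected from the screw; these can also follow the operation, so the expected-event list does not separate the two sources either.

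**The case against.** The strongest reply is that nothing here compels a grade. Clinical judgment is part of the stated basis. *Unlikely* mentions other concomitant treatments, which can be read to include harvest and femoral fixation. *Not Related* accepts any definitively documented cause: pain located at the harvest site is an example a surgeon could document. Timing is only an example of evidence under *Potentially*, which is the category for uncertainty, and using it when causes cannot be separated is an honest record. Always suspecting the device is a deliberately cautious stance. Other causal factors are recorded, events are also shown by organ class and preferred term, and no safety hypothesis or threshold depends on a device-related rate. Nor does the protocol say that *Potentially* will be pooled with the higher grades.

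Most of this stands, and it rules out two stronger readings that a reader might infer. One is that every early surgical event must be counted as device-related; judgment and the *Not Related* route prevent that. The other is that the study cannot describe the screw's safety at all; the relationship table is one display among several.

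What does not stand is that the wording is therefore harmless. The concomitant-treatments example sits inside the second condition of *Unlikely*, and the first still fails for any event with compatible timing. Free judgment without a place to record procedure-relatedness leaves that judgment unreported. Nor is this a matter for the SAP, which cannot tabulate a procedure grade that was never collected.

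**Conclusion.** The point holds in this limited form: with a single grade against the screw and drug-type definitions, early postoperative events and true screw reactions are both likely to be graded *Potentially Related*. The relationship table in VII.4.4 therefore cannot reliably separate screw-related from procedure-related events and may overstate the former.

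The size cannot be quantified from the protocol, which gives no rate for postoperative events and no indication of how the investigator would grade them. The conclusion rests on the definitions being applied roughly as worded and on definitive alternative causes often being unavailable for non-specific events. The co-primary analyses are not touched. The weakness bears on a stated secondary objective in a single-arm study whose data are intended chiefly for regulatory use (XII.1), so it should be corrected.

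**What to change.** In VI.3.3.2:

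- Grade each adverse event twice: relationship to the screw, and relationship to the surgical procedure, defined to include graft harvest, bone tunnels and femoral fixation.
- Let *Unlikely* be met when the procedure is the more plausible explanation, even if the timing is compatible with the screw.
- Name the procedure as an accepted alternative cause under *Not Related*.
- Replace the dechallenge, rechallenge and trial-medication wording with criteria suited to an implant, and use one term for the object being graded, here and in VII.4.4.

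In VII.4.4, tabulate treatment-emergent events by both gradings.

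The cost is one extra eCRF item per adverse event and one extra column in the tables. Some events will still be attributable to either source; the two gradings make that visible instead of assigning them to the screw by default.
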